15. RISK MANAGEMENT PROCEDURES AND ADEQUACY OF RESOURCES

The overall risks of this proposal are small. Protection of subject confidentiality and privacy will be rigorously guarded by the assignment of coded numbers to each file in the computer analysis and database. Resulting data will not be released to any subject, and released only to a patient's primary physician when an appropriate release form is signed by the patient. The UCSD psychophysiology research laboratory of [name] has studied over 1000 control subjects and patients without any problems with confidentiality.

For the drug evaluation study, risk management procedures include: 1) Subjects will be asked to refrain from alcohol or other drug use while on the study. 2) Each subject will receive a complete history and physical examination prior to acceptance into the study. 3) A battery of psychological tests will be administered, as will an EKG and urine toxicology screen (which will also be used to test for pregnancy in drug studies including women of childbearing potential). 4) Subjects involved in studies with drugs will arrange for their transportation from the hospital, and any subject reporting any sedation upon completion of the study will be instructed to not operate a motor vehicle until the sedation is resolved. Subjects known or determined to have cardiovascular disease by EKG or patient history will be excluded. All subject information will be kept in a secure and locked area of the laboratory, CTF Building, UCSD Medical Center. Confidentiality will be protected to the extent provided by law.

If a participant has any questions regarding the study, they may contact the PI, [name]., Ph.D., Monday-Friday, 8 a.m. – 4:30 p.m. at [contact]. He may be reached after hours by contacting the UCSD operator at [contact] and having them page [name]. If any emergencies arise related to participating in these studies, the participant may proceed to the nearest emergency room or call 9-1-1.

Subjects will be told that they can terminate the experiment at any time if an aspect of the procedure causes them discomfort.

Risks associated with specific study populations: Because the proposed studies include schizophrenia patients, it is important to consider any risks that might be specifically elevated in this study population. As noted above, clinical trials with schizophrenia patients in which daily dosing of 10 - 20 mg memantine was added to ongoing medications have generally reported no or minimal evidence of either clinical improvement or adverse events. Thus, the likelihood that a single pill of 10 - 20 mg memantine would be associated with clinical changes is low. The population of schizophrenia patients to be enrolled in these studies will come primarily or exclusively from subjects who are seeking enrollment in an existing protocol

for supported employment (#071306, [name], PI); based on this, they will most likely be high functioning, clinically stable, and (by definition) seeking employment. Nonetheless, should the subjects voice any thoughts of self-harm or suicidality, all testing staff are instructed to immediately contact the licensed physician who is on-site and covering each test session. The physician will then immediately evaluate the subject, and based on their clinical condition, might escort them across the street to the Emergency Room at the UCSD Medical Center for further evaluation and, if necessary, treatment. It is important to note that, in over 30 years of testing schizophrenia patients at the CTF in the laboratories of Drs. [name] and [name], including several thousand schizophrenia patients and several drug challenge studies, only 1 subject has ever required an escort to the UCSDMC Emergency Room.

16. PRIVACY AND CONFIDENTIALITY CONSIDERATIONS INCLUDING DATA ACCESS AND MANAGEMENT

All data and specimens are de-identified, and coded numbers are assigned to each file in the computer analysis and database. Research records are kept in a room separate from the data and specimens. Both the separate room and the filing cabinet containing the records are locked. Only the study coordinator has the key to access the files. Subject unique identifiers (name, DOB, SS#, etc.) will never be connected with the de-identified data. When published, data will remain de-identified, though subjects' non-unique demographic information (age, sex, ethnicity, handedness, diagnosis) may be reported together with the de-identified data. No other information will be provided to entities beyond the PI and key personnel noted in this application. The PI's UCSD research laboratory has studied over 1000 subjects and patients without any problems with confidentiality.

Positive drug screen results, if they became known outside the research, could reasonably place the subject at risk of criminal civil liability or be damaging to the subject's financial standing or employability. There is also the possibility of loss of confidentiality. Research records will be kept confidential to the extent allowed by the law. A study number will be used to identify information from participants. The database that relates the participants to a specific study number will be maintained using initials. Any database file will be encrypted on a password-protected computer.

All recruitment, interviewing, consenting, physical examinations and testing will take place in a private setting, specifically a dedicated interview room at the UCSD Medical Center, occupied only by the interviewing staff, physician and test subject, with the door closed, and a "DO NOT DISTURB" sign posted on the door.

It is NOT reasonably foreseeable that the study will collect information that Federal, State, and/or local laws/regulations requires to be reported to other officials (e.g., child or elder abuse; positive results from lab tests). However, as is true of any clinical population, and particularly in patients with brain disorders, it is possible that subjects may exhibit severe psychiatric symptoms including the description of suicidal ideation. An on-call licensed physician is covering all studies; should any such clinical issues arise, the covering physician will be contacted and will assess the situation for the most appropriate clinical intervention.

17. POTENTIAL BENEFITS

The information gained in these studies is expected to lead directly to a greater understanding of the pathophysiology of serious illnesses, and will facilitate the development of novel treatment strategies. For the drug evaluation study, those likely to benefit most from the proposed project are severely ill psychiatric patients, as enhanced understanding of their cognitive and neurochemical abnormalities will allow for more accurate assessment and treatment of their symptoms. Individual subjects will benefit from a medical and psychological evaluation. Control subjects are unlikely to receive any other direct benefits from the proposed study other than the opportunity to contribute to efforts designed to relieve human suffering; there is evidence that participation in generative activities that improve self-esteem can have a positive impact on an individual's quality of life. Individuals with schizophrenia may or may not benefit from the long term goal of their study: to identify medications that will enhance the clinical impact of cognitive interventions in psychiatric patients.

18. RISK/BENEFIT RATIO

For the drug evaluation study, the risks from study participation include mild discomfort from drug effects, and the benefits include careful medical evaluation and potential gains in self-esteem among study participants, and significant benefit to patients in terms of knowledge gained related to the nature and optimal treatments of psychiatric disorders. The risk-benefit ratio of this study is very low.

19. EXPENSE TO PARTICIPANT

N/A

20. COMPENSATION FOR PARTICIPATION

The subjects will be paid \$30 for the SCREENING SESSION and \$130 for completion of the TEST SESSION. These payments have been accepted by the Human Subjects Committee as reasonable amounts for the length of subject participation. Subjects that participate in the "WITHIN-SUBJECT" study will be paid \$30 for the SCREENING SESSION, \$100 after the first test day and \$130 for the completion of the second test day. This is a total of \$260. Subjects will be reimbursed for parking costs on the SCREENING and TEST days and given breakfast and lunch on the TEST day.

Participants in the ONE-DAY study will be paid a total of \$30. Compensation will be prorated to \$10 per hour if the following happens: participants do not pass the tests; participants voluntarily withdraw from the study; or study personnel withdraw participants from the study.

24. BIOLOGICAL MATERIALS TRANSFER AGREEMENT

NA

25. INVESTIGATIONAL DRUG FACT SHEET AND IND/IDE HOLDER

NA

26. IMPACT ON STAFF

NA

27. CONFLICT OF INTEREST

NA

28. SUPPLEMENTAL INSTRUCTIONS FOR CANCER-RELATED STUDIES

NA

29. OTHER APPROVALS/REGULATED MATERIALS

NA

30. PROCEDURES FOR SURROGATE CONSENT AND/OR DECISIONAL CAPACITY ASSESSMENT

Schizophrenia patients who have been identified for participation in our studies will also be enrolled in IRB-approved clinical trials of cognitive training with [name]. [name] has approval to screen and administer surrogate identification process. Any patients that have been identified as having impairment in their decision-making ability will be determined by [name] and will not be referred to our studies.

Revision date: October 29, 2010

Statistical Analysis Plan

Biomarker Strategies for Medication-Enhanced Cognitive Training in Schizophrenia

NCT01555697

NIMH-R34-MH093453-NS

Latest IRB approval date: August 17, 2019

IRB expiration date: August 15, 2020

The primary statistical considerations for these data are those required to test the primary hypothesis that memantine (MEM) would enhance sensorimotor gating and neurocognition in schizophrenia (SZ) patients. The operational measure of sensorimotor gating was prepulse inhibition of startle (PPI). The primary hypothesis was tested by a 2-way repeated-measure ANOVA of PPI with MEM dose and prepulse interval (10, 20, 30, 60 or 120 ms) as within-subject factors. The key dependent measure was %PPI, calculated according to common practices in the literature. The hypothesis that MEM will increase PPI in SZ patients was to be confirmed by a significant main effect of drug (active > PBO) or significant interaction among the variables of drug, dose (10 or 20 mg), diagnosis (healthy subject (HS) or SZ) or prepulse interval, and informative post-hoc comparisons. The assumptions behind these analyses range from the standard assumptions underlying the use of parametric analyses, to those specific to prepulse inhibition, e.g. related to the potential confounding effects of drug or diagnosis effects on startle magnitude. Data were demonstrated to be normally distributed and drug effects on PPI were shown to be independent of changes in startle magnitude. Analyses confirmed the hypothesis for the 20 mg dose of MEM in SZ patients.

The same general analytic approach was applied towards MEM effects on neurocognition, assessed via the MATRICS Comprehensive Cognitive Battery (MCCB). Here, neurocognitive domain (7 domains) was a within-subject variable along with drug (active vs. PBO), and diagnosis and dose were between-subject factors. The dependent measure was MCCB T-score for each of the 7 domains, as well as a single comprehensive T-score. The hypothesis that MEM will increase MCCB scores in SZ patients was to be confirmed by a significant main effect of drug (active > PBO) or significant interaction among the variables of drug, dose (10 or 20 mg), diagnosis (healthy subject (HS) or SZ) or MCCB domain, and informative post-hoc comparisons. Again, the assumptions behind these analyses range from the standard assumptions underlying the use of parametric analyses, to those specific to neurocognitive performance, e.g. related to the potential confounding effects on levels of consciousness (i.e. increasing or decreasing alertness). Data were demonstrated to be normally distributed and drug effects on MCCB were shown to be independent of changes in self-assessed drowsiness. Analyses failed to confirm the hypothesis that MEM acutely enhanced neurocognition, in either HS or SZ patients.

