2. To assess the effects of the NMDA antagonist, memantine, on PPI and neurocognition in healthy subjects, and the moderating roles of personality and genotype in these effects. 30 healthy subjects will complete a within-subject study of placebo vs. 20 mg memantine (p.o.) on two separate days, completing measures of sensorimotor gating and neurocognition on each test day. All subjects will be characterized in terms of specific genetic and personality characteristics.

3. To assess the effects of the NMDA antagonist, memantine, on PPI and neurocognition in schizophrenia patients, and the moderating roles of genotype in these effects. 60 well-characterized and clinically stable individuals with schizophrenia will complete a within-subject study of placebo vs. 10 mg memantine (p.o.) (n=30) or placebo vs. 20 mg memantine (n=30) on two separate days, completing measures of sensorimotor gating and neurocognition on each test day. All subjects will be characterized in terms of specific genetic characteristics.

Figure 1. Schematic "flow chart" of current studies

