impaired cognitive or sensorimotor inhibition. Thus, our laboratory and others have reported impaired PPI in patients with Schizophrenia, Obsessive Compulsive Disorder (OCD), Huntington's Disease, nocturnal enuresis and Attention Deficit Hyperactivity Disorder or Tourette's Syndrome. These disorders are all characterized by a loss of gating in sensory, motor or cognitive domains, and are characterized neurologically by abnormalities in cortico-striato-pallido-pontine circuitry that modulates PPI.

Over the past 20+ years, the PI and colleagues have systematically studied the neural substrates of PPI in rats. These studies have revealed that PPI is regulated by sequential neural connections between limbic cortex (temporal and medial prefrontal cortex), the ventral striatum, the ventral pallidum and the pontine tegmentum. This limbic cortico-striato-pallido-pontine circuitry then interfaces with the primary startle circuit at the level of the nucleus reticularis pontis caudalis. The neurotransmitters active at each level of this circuitry have been studied as well: the cortico-striatal interface involves interactions between glutamate and D2 dopamine receptors; the striato-pallidal input is GABAergic, as is the pallido-pontine input. Thus, by identifying patterns of PPI deficits in neuropsychiatric populations, we are able to use this information to understand the pathophysiology of these disorders, as well as to develop strategies for designing optimal drug treatments. We have already made significant steps towards these ends.

Some evidence already suggests that findings from preclinical studies of the neural substrates regulating PPI can "cross species" and be applied to humans. For example, PPI is disrupted in patients with Huntington's Disease (HD), and in rats with cytotoxic lesions of striatal regions that model features of the pathophysiology of HD. Preliminary studies suggest that the "cross-species" parallels of this measure can also be demonstrated with pharmacologic probes: PPI is disrupted in both rats and humans by indirect DA agonists (e.g. amphetamine) and by direct DA agonists (e.g. bromocriptine and apomorphine). These pharmacologic studies of PPI in humans are not fully compelling at this time, since they were either performed only in small samples, or in patients with neurologic disorders (e.g.. Parkinson's Disease) that might complicate interpretation of the findings as they relate to the normal neural regulation of PPI.

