d) Subject payment (also see below, section 18): For subjects participating in the "Within-Subject" test sessions, payment will be divided in the following schedule: on completion of screening day: \$30; on completion of first TEST SESSION day: \$100; On completion of second TEST SESSION day: \$130. This payment schedule provides appropriate incentive for the subjects to return for the second test day. This is to ensure that subjects return for the second and third test days. If subjects fail screening criteria for recreational drug use prior to any TEST SESSION day, they will not be tested further and will not be paid for that test day. We will recommend that subjects remain in our laboratory for monitoring until six and one half hours after pill ingestion. Should they choose to leave our facility for any reason prior to that time, it will be at their own risk. Their involvement in the study will be completed and payment on the Test Session day will be prorated to \$16 per hour.

e) Venopuncture: Venopuncture for COMT allelic testing in some subjects will occur during the initial visit, before or after what normally is titled the SCREENING SESSION in the studies listed below. A single venopuncture performed by certified individuals within the UCSD Medical Center GCRC/CTRI or Blood Drawing Station will be used to 10 cc of blood for COMT allelic testing. Based on specific needs of the experimental design (e.g. equal number of Met/Met, Val/Met and Val/Val allelic carriers, or subgroups of "high" vs. "low" PPI levels, based on the upper vs. lower quartile of a normal population distribution), subjects may be asked to come back for further testing, if they indicate they would like to do so. If participants continue to the remainder of the study, there will be 2 test days, one of which will involve placebo, and the other day involving an active dose of amphetamine (20 mg), memantine (20 mg) or other approved test drug/dose. The TEST SESSIONS will mimic those in the WITHIN-SUBJECT model below; however, venopuncture occurs only during the first visit.

f) Clinical assessment: Specific clinical assessment tools used in control and schizophrenia subjects are described in Section 10.

g) Test schedules:

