For example, to assess the effects of memantine on "gating" measures in schizophrenia patients, the primary measure will be evaluated by 2-way repeated-measure ANOVA of PPI with memantine dose and prepulse interval as within-subject factors. The hypothesis that memantine will increase PPI in schizophrenia patients will be confirmed by a significant effect of dose (active > PBO) or significant dose x interval (int) interaction and post-hoc comparisons at one or more prepulse intervals. Existing data (see above) provide a strong *a priori* prediction that the 120 ms prepulse interval will be most sensitive to PPI-enhancing effects of MEM. The effect size (d) for PPI-enhancement by 20 mg memantine in HCS was 0.91; with a similar "d" in patients, 30 patients/dose yields power of 0.92 to detect the predicted memantine effects; with maximum expected attrition (n=24), power is 0.85. Past findings also lead to the prediction that these MEM effects would be most robust in subjects exhibiting the lowest basal PPI levels (d=1.80). Using a median split of mean basal (screening) PPI levels, ANOVA as above will detect a significant interaction of memantine dose x basal PPI level, or dose x basal level x int, and significant post-hoc comparisons at one or more prepulse intervals (again, 120 ms being the strongest *a priori* candidate). Given the published "d" in control subjects, a comparable "d" in the proposed 12-15 "low PPI" patients/dose group would yield power >0.95 to detect the predicted memantine effects.

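### The SAP lets a drug-by-diagnosis interaction confirm that memantine raises PPI in schizophrenia patients, although such an interaction neither shows a drug effect in patients nor separates diagnosis from basal PPI

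*SAP*

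**What the plan says.** The protocol treats the patient question as a within-patient one. Aim 3 (Section 6) says "60 well-characterized and clinically stable individuals with schizophrenia will complete a within-subject study of placebo vs. 10 mg memantine" or, in the other half of the sample, placebo against 20 mg, with 30 patients per dose. Section 9.j names the primary test as a "2-way repeated-measure ANOVA of PPI with memantine dose and prepulse interval as within-subject factors". Diagnosis is not in that model. Healthy subjects belong to a separate aim (Aim 2), with 30 subjects at 20 mg only.

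The SAP opens with the same kind of test, a "2-way repeated-measure ANOVA of PPI with MEM dose and prepulse interval (10, 20, 30, 60 or 120 ms) as within-subject factors". Its rule for confirming the SZ hypothesis is wider. A main effect of drug in the right direction will do, and so will a "significant interaction among the variables of drug, dose (10 or 20 mg), diagnosis (healthy subject (HS) or SZ) or prepulse interval", in either case with informative post-hoc comparisons, which are not specified.

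Two other protocol statements bear on the diagnosis factor. Section 7 says that "our laboratory and others have reported impaired PPI in patients with Schizophrenia". Section 9.j gives the basis for the expected effect: "The effect size (d) for PPI-enhancement by 20 mg memantine in HCS was 0.91". It then predicts that the effect will be "most robust in subjects exhibiting the lowest basal PPI levels (d=1.80". The protocol plans a median split on screening PPI to examine this in patients. The SAP does not mention basal PPI; the only PPI-specific confounder it names is startle magnitude.

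**The concern.** There are two separate problems with counting a diagnosis interaction as confirmation.

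First, it answers another question. Drug x diagnosis compares the drug effect in SZ with that in HS. It can be significant when memantine works in healthy subjects and does nothing in patients. The required direction (active above placebo) is attached to the main effect of drug, not to the interactions.

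Second, the interaction is open to a composition effect. If PPI is lower in patients, and memantine acts mainly at low PPI, the average drug effect will differ between the groups even when patients and healthy subjects with the same basal PPI respond identically. The programme is about PPI as a biomarker of response, so a reader will want to know whether schizophrenia or low PPI goes with the larger response. The SAP as written does not separate the two.

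**Working it through.** **Inputs from the documents.** Overall d=0.91 at 20 mg in healthy subjects; d=1.80 in those with the lowest basal PPI; 30 patients per dose; 30 healthy subjects at 20 mg; alpha 0.05 (two-sided assumed).

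**Assumptions not in the documents.** Half of the healthy subjects count as low PPI; the two halves share one SD; a stated share p of patients falls below the control median; the SD of the drug-minus-placebo change is 1.41 or 1.0 raw SD, from √(2(1−r)) with test-retest r=0 or 0.5.

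**Step 1: the plan's own figure.** A noncentral t calculation that treats active and placebo as two independent groups gives power 0.934 at n=30 and 0.870 at n=24. The protocol states 0.92 and 0.85, so its figures reproduce to within two points. They concern the drug effect; no power is given for a diagnosis contrast.

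**Step 2: what the interaction estimates.** Drug x diagnosis = (active − placebo in SZ) − (active − placebo in HS). Take an SZ effect of 0 and an HS effect of 0.91. The contrast is −0.91. Its standard error with 30 v 30 is SD × √(2/30), which is 0.26 for SD 1.0 and 0.37 for SD 1.41. The ratios are about 3.5 and 2.5 in absolute value, both beyond the 5% critical value of about 2.0. An interaction of that kind is likely to be significant when the drug has no effect in patients.

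**Step 3: composition.** With equal halves and a common SD, the high-half effect is 2 × 0.91 − 1.80 = 0.02. If response depends only on basal PPI, the expected SZ minus HS difference in drug effect is (p − 0.5) × (1.80 − 0.02).

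**Step 4: rejection rate.** Simulated t-test on change scores, 30 v 30, 20,000 trials per setting, with no diagnosis effect at a given basal PPI:

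| Patients below control median | Expected difference (SD) | Rejection, change SD 1.41 to 1.0 |
|---|---|---|
| 50% | 0 | about 5% |
| 60% | 0.1 × 1.78 = 0.18 | 7-8% |
| 75% | 0.25 × 1.78 = 0.45 | 18-26% |
| 85% | 0.35 × 1.78 = 0.62 | 31-46% |

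Once the model includes the drug x basal-PPI term, rejection returns to about 5% throughout. That run took the low/high stratum as known without error.

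**Step 5: sensitivity to the high-half effect.** Raising it from 0.02 to 0.5 lowers the rate at 70% low (r=0.5) from 18% to 13%. The common-SD assumption also matters. If the low-PPI subgroup's SD were 0.77 of the overall SD, its raw effect would be 1.80 × 0.77 = 1.39 and the high half 1.82 − 1.39 = 0.43; the rate at 75% low is then 9-14%. At an SD ratio of 0.60, the effects are 1.08 and 0.74, and the rate is about 6%.

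**Step 6: the within-patient test.** At 75% low, the mean effect in patients is 0.75 × 1.80 + 0.25 × 0.02 = 1.36 SD. This is a real drug effect, and the within-patient test detects it in over 99% of simulated trials. The HS/SZ mix plays no part in that test.

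**The case against.** The strongest reply is that the SAP's claim is about patients and its named primary test is within-subject. Each patient is compared with his or her own placebo day, so the make-up of the healthy group cannot bias the result. The SAP reports confirmation for 20 mg in SZ and does not say that this rests on a diagnosis interaction. The rule also requires informative post-hoc comparisons, and the protocol already plans a basal-PPI split within patients. All of this stands. It limits the point to the wording of the rule and to how a diagnosis interaction may be read. The post-hoc requirement is only a partial safeguard, because the comparisons are not specified.

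A reader might infer that healthy subjects have become a second comparator. They have not: placebo within each subject is the comparator, and diagnosis is a between-subject factor. A reader might also take 18-26% as a false-positive rate for the SZ hypothesis. It is not. It is the rejection rate under no diagnosis effect at a given basal PPI, a null that the SAP does not state; in the same scenario memantine truly raises PPI in patients.

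It is also fair to say that the illustration is fragile. The 0.02 and the shares of low-PPI patients are assumptions, and Section 15 expects patients who are mostly high functioning and stable. Recall by PPI level (Section 9.e) is only permitted, and nothing shows that it was applied differently to the two groups. Finally, Section 7 presents low PPI as a feature of the disorder, so adjusting for it changes the question and does not simply remove a nuisance.

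**Conclusion.** The point holds in a limited form. The SAP's rule accepts an interaction with diagnosis as confirmation of a drug effect in patients, which the protocol's patients-only model does not do and which such an interaction cannot show. If one appears, it may reflect basal PPI, and the SAP has no analysis to examine that. The harm is misattribution to diagnosis, not a false memantine effect in SZ. Nothing in the documents undermines the reported 20 mg result on this ground.

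The size of the risk cannot be determined. It is nil if basal PPI is balanced between the groups. Under the assumptions set out above it grows with the share of low-PPI patients, and it shrinks as the high-half effect rises. Calling basal PPI the strongest moderator would go too far. It has the largest stated d (1.80, against an estimated 1.53 for COMT genotype and 1.27 for novelty seeking), but Section 9.j describes COMT genotype as a critical moderating factor and gives no high-PPI figure beside the 1.80.

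**What to change.** 1. Base confirmation of the SZ hypothesis on the drug-placebo contrast within SZ, separately for 10 and 20 mg, and take interactions with diagnosis out of the confirmation rule.
2. Report drug x diagnosis as a secondary analysis in the 20 mg groups only, since Aim 2 plans no healthy subjects at 10 mg. Give it both without and with continuous screening PPI, on one scale common to HS and SZ, and its interaction with drug. A main effect of screening PPI alone would not be enough. Present estimates and confidence intervals for both versions.
3. State that the two versions answer different questions, because low PPI may be part of the disorder. Do not infer a cause from whether the adjusted term is significant: losing significance may reflect lost precision, and noise in screening PPI can leave residual confounding. Note also that diagnosis cannot be separated from ongoing psychotropic medication, because Section 11 excludes controls who use it and sets no such exclusion for patients.

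The cost is SAP wording and one covariate with its interaction, using screening PPI that the protocol already plans to measure. The adjusted contrast will have a wider interval. As the SAP already reports results, the added analyses should be labelled post hoc.

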j. Statistics: Tests for homogeneity of variance are performed, and if appropriate, analyses of variance (ANOVA) used. Statview/Superanova software is used on the Macintosh. For startle data, P-Alone amplitude, PPI and startle latency are analyzed by ANOVAs; for drug studies, drug dose is used as a within-subject factor. Habituation is detected by a significant effect of trial block. Visuospatial priming is analyzed separately for baseline, facilitation, and inhibition conditions using ANOVAs. Baseline is a measure of visuospatial response time, while facilitation and inhibition scores are measures of sensorimotor modulation. Nonparametric statistics are used for the Latent Inhibition analyses because data from this test tend toward a bimodal distribution. A rank sum factorial analysis is used for the data. Other dependent measures will be analyzed with parametric or non-parametric analyses, generally consisting of mixed design ANOVAs, as appropriate. Following a significant ANOVA, specific comparisons are made using Tukey's tests. Alpha is 0.05.

Power considerations: Sample sizes vary across the different studies, based on issues ranging from the study design and goals to empirical evidence for effect sizes with the proposed drug or measure. For example, "ONE-DAY" studies are designed to identify and "pilot" optimal stimulus parameters for testing specific hypotheses, and these studies may not be powered to achieve traditional levels of statistical significance. On the other hand, designing studies of drug effects on PPI and related measures in control or patient populations requires detailed power information.

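### The SAP's rule for confirming that memantine raises PPI in schizophrenia patients uses diagnosis and dose interactions that its named two-way model cannot contain, and ties no test to those patients

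*SAP*

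**What the plan says.** The SAP's paragraph on PPI contains three statements that have to be read together.

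- **Model.** The primary hypothesis was tested by a "2-way repeated-measure ANOVA of PPI with MEM dose and prepulse interval" as within-subject factors, with five intervals from 10 to 120 ms. No between-subject factor is named and the analysis population is not given.
- **Rule.** The SZ hypothesis is confirmed by a drug main effect (active above placebo) or by a significant "interaction among the variables of drug, dose (10 or 20 mg), diagnosis (healthy subject (HS) or SZ) or prepulse interval, and informative post-hoc comparisons".
- **Result.** "Analyses confirmed the hypothesis for the 20 mg dose of MEM in SZ patients".

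The SAP's paragraph on neurocognition begins "The same general analytic approach was applied towards MEM effects on neurocognition". There, "diagnosis and dose were between-subject factors", and the rule has the same form: "The hypothesis that MEM will increase MCCB scores in SZ patients was to be confirmed by a significant main effect of drug", or an interaction.

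Protocol section 9.j sets a narrower rule for PPI. It applies to patients, requires an effect of dose (active above placebo) or a dose-by-interval interaction with post-hocs at one or more prepulse intervals, and names 120 ms as the strongest a priori candidate. Each dose group is to be analysed independently; pooling of doses is reserved for exploratory work. On post-hocs in general: "Following a significant ANOVA, specific comparisons are made using" Tukey's tests, with alpha 0.05.

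**The concern.** The rule counts effects that the named model cannot produce. Under Aim 3 in protocol section 6, each patient receives placebo and one active dose, so 10 versus 20 mg is a comparison between patients. Diagnosis is between-subject by nature. In the two-way model, memantine dose can only mean active versus placebo. Some other model must therefore supply the diagnosis and dose terms, and the PPI paragraph does not describe it.

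The rule is also not anchored to the population it concerns. SZ patients appear in the hypothesis and as one level of diagnosis, but no test is confined to them. A drug-by-diagnosis interaction has no sign: it is what one would expect to see if healthy subjects respond and patients do not. The post-hocs that accompany an interaction need only be informative, with no group, contrast, interval or direction given. The sentence does not make clear whether the post-hoc clause also applies to the main-effect route.

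At stake is the trial's positive primary claim. A reader cannot tell from the SAP which test supports it.

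**Working it through.** **1. Protocol and SAP side by side**

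| Element | Protocol 9.j | SAP, PPI |
|---|---|---|
| Population | Patients | Not stated for the model |
| Dose groups | Analysed independently | Separation not repeated |
| Main-effect route | Active above placebo | Active above placebo |
| Interaction route | Dose by interval, no direction | Any among drug, dose, diagnosis, interval, no direction |
| Post-hocs | At prepulse intervals, 120 ms the leading candidate; Tukey | Informative; no contrast named; 120 ms not singled out |

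The SAP thus adds the diagnosis and dose routes, loosens the post-hoc requirement, and does not repeat the 120 ms prediction or the per-dose separation. The undirected drug-by-interval route is already in the protocol.

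**2. Inputs**

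- Planned sizes (protocol section 6): 30 SZ at 10 mg, 30 SZ at 20 mg, 30 healthy subjects at 20 mg. The SAP gives none.
- d = 0.91 for PPI in healthy subjects at 20 mg; stated power 0.92 at n = 30 and 0.85 at n = 24 (protocol 9.j).
- Alpha 0.05, taken as two-sided.

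**3. The protocol's own power figure**

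For a paired t-test the noncentrality is dz × √n on n − 1 df.

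- Taking dz = 0.91/√2 ≈ 0.64: 0.64 × √30 = 3.51, power 0.92; 0.64 × √24 = 3.14, power 0.85. Both stated figures are reproduced.
- Taking 0.91 itself as dz: power 0.998 and 0.989, which do not match.

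So 0.64 is the main assumption, with 0.91 as the upper case.

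**4. Healthy subjects respond, SZ patients do not: how often is the SZ hypothesis confirmed?**

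*Reading A: two-way model in SZ 20 mg patients only.* By construction the directional main effect is falsely positive 2.5% of the time. Simulation (6,000 runs per scenario, five intervals, inter-interval correlation assumed) gave 2-3% for the main effect and 2-4% with the interaction route and Tukey added.

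*Reading B: pooled ANOVA, adjusted SZ contrast always required.* The same simulation gave, for SZ 20 mg, about 2% with Bonferroni and 0.2-4.8% with Tukey, depending on the error term.

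*Reading C: pooled drug main effect accepted with no SZ contrast.* With dz on the interval mean, unit SD of the difference score and 30 per cell, noncentrality is the pooled mean over its standard error:

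- three cells weighted equally: (dz/3)/√(1/90) = dz × √10, 87 df;
- the two 20 mg cells only: (dz/2)/√(1/60) = dz × √15, 58 df;
- healthy and SZ weighted equally, SZ averaged over doses: (dz/2)/(½√(1/30 + 1/60)) = dz × √20, 87 df.

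| Layout | Noncentrality, dz 0.64 | Rate, dz 0.64 | Rate, dz 0.91 |
|---|---|---|---|
| Three equal cells | 2.02 | 52% | 81% |
| Two 20 mg cells | 2.48 | 68% | 93% |
| Healthy = SZ weight | 2.86 | 81% | 98% |

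With 24 per cell and three equal cells, the first rate falls to 43% at dz 0.64.

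**The case against.** The case against is substantial. Only reading C does real damage, and it fits the reported results least well. A pooled main effect cannot by itself single out one dose in one diagnosis group, yet the PPI conclusion is specific to both. The neurocognition conclusion is also stated by group: "Analyses failed to confirm the hypothesis that MEM acutely enhanced neurocognition, in either HS or SZ patients". Some group-level test was evidently made. Pooling for PPI is stated nowhere; it is inferred from the neurocognition model. The SAP's PPI model closely follows the protocol's patients-only analysis, and the SAP withdraws neither that analysis nor the Tukey tests. On that view the main effect is already specific to SZ patients. The reading C rates also depend on a cell layout that the SAP does not give.

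Most of this stands as a limit on consequence. It does not remove the mismatch between model and rule. If the model was patients-only, diagnosis has no place in the rule; if diagnosis belongs in the rule, healthy subjects were in a model that is not described. The protocol cannot simply be read in, because the SAP states a different rule.

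A reader might go further and infer that the 20 mg SZ finding is a false positive carried by healthy subjects. The documents do not support that: the wording of the conclusion points to an SZ contrast, even though the SAP does not identify it. Nor was anything falsely confirmed on the MCCB, where the result was negative.

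**Conclusion.** The point holds as a fault in the stated decision rule. That diagnosis and 10 versus 20 mg cannot be in the named model, that the interactions carry no direction, and that neither the main effect nor the post-hocs are tied to SZ patients all follow from the text and the design, with no assumption needed.

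The size of the consequence is conditional. Under readings A and B there is little or no inflation for SZ 20 mg. Under reading C, a response in healthy subjects alone meets the rule in roughly 50-80% of cases at dz 0.64 and 81-98% at dz 0.91, assuming 30 per cell, no effect in either SZ group and one of the three layouts shown. Which reading was used cannot be settled from the SAP, so the reported result is neither impugned nor fully documented. The rule should be corrected.

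**What to change.** Base the SZ conclusion on the analysis already in protocol 9.j: %PPI, active versus placebo, in SZ patients only, separately for the 10 mg and 20 mg groups. Count the hypothesis as confirmed in a dose group by either

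- a drug main effect with active above placebo; or
- a drug-by-interval interaction with a Tukey-adjusted post-hoc in SZ patients showing active above placebo, 120 ms being the a priori interval.

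Label main effects pooled over healthy subjects and SZ patients, and all diagnosis or dose interactions, as secondary, and describe the model they come from. Then state whether the 20 mg SZ conclusion holds under this test.

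The cost is a change of SAP wording and a re-analysis of data already collected. The protocol's power of 0.92 (0.85 at n = 24) still applies, because it was calculated for patients per dose group. Findings that rest on the other interactions become exploratory. Because results are already reported, this should be presented as a re-analysis, not as pre-specification.
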